## PROTOCOL SUMMARY

Title	Retrospective evaluation of treatment durability among treatment-naive HIV-infected individuals initiated first-line ART in Russia
Supplier	Atlant Clinical Ltd
Rationale	Treatment durability is an important factor in HIV disease management since HIV infected individuals need to take ART life-long. To date, there is limited data on treatment durability in HIV infected individuals initiating ART in Russia. Understanding the durability of treatment is essential for improving medical care of patient living with HIV.
Primary Objective	To evaluate the 48 weeks treatment durability among treatment naive HIV-infected individuals determined as a percentage of patients remained on initial therapy
Study Design	A non-interventional retrospective study.
Study Population	Treatment-naive at the time of initiation of ART with NNRTI plus two NRTIs or PI boosted by ritonavir with 2 NRTIs per usual standard of care of the investigator in AIDS clinics of Russia.
Study Duration	Up to 24 months will be dedicated to retrospective data collection and analysis from treatment-naïve HIV-infected patients who initiated their first-line ART between February 01 and June 30, 2017
Exposure and Outcome	Initial ART per usual standard of care in AIDS clinics of Russia: NNRTI plus 2 NRTIs or PI boosted by ritonavir with 2 NRTIs. Treatment durability determined as a percentage of patients continuing their first-line for 48 and 96 weeks without changes (switch or withdrawal) evaluated retrospectively
Statistical Methods	Data will be presented descriptively as follows: the number of observations, mean and standard deviation, median, first and third quartiles, minimum and maximum for continuous variables, and the absolute frequencies and percentage of patients presenting the given feature for qualitative variables. The results on the study endpoints (proportion of patients who remain on first-line ART at 48 and 96 weeks) will be presented with two-sided 95% confidence intervals. Univariate and multivariate logistic regression will be used to study the association between patients' baseline demographic and clinical characteristics and treatment discontinuation status.

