Sample Size and Power Calculations	1000 patients. The assumed 1-year (approximately 48 weeks) discontinuation rate, based on published research, is 30% [20] therefore the assumed proportion of patients who remain on the first line ART regimen at 48 weeks is 70%. Inclusion of 1000 patients will allow the estimation of this proportion with 95% CI: Lower bound - 67.2%, Upper bound – 72.8%, Actual width (precision) - 5.7% ( $\pm 2.8\%$ ).
Limitations	In this a retrospective study the quality of the data is important. And the potential issue of missing data is a limitation of the study. Therefore, it is important for the sponsor or designee to monitor data completion and perform quality checks during the study. To minimize missing data, a set of core variables is required to be available at enrollment as part of inclusion criteria.

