## 1.2 Rationale

The Russian MoH has recently initiated a national program aimed to increase the proportion of HIV diagnosis and linkage to care of HIV infected individuals. Treatment durability is an important factor in HIV disease management since HIV infected individuals need to take ART for many years. [5] To date, there is limited data on treatment durability in HIV infected individuals initiating ART in Russia. Understanding the durability of treatment is essential for improving patient management in order to achieve the goals set by the Russian MoH and the HIV elimination goals set by the WHO.

According to the robust clinical studies data, there was significant increase of CNS AEs in groups of patients treated with EFV [14]. As with other NNRTIs, drug interactions and a low resistance barrier have to be considered. Novel NNRTIs such as etravirine and rilpivirine were implemented in routine clinical practice in Russia recently and have higher cost which may influence access and therefore durability to this third drug medications.

Observational studies, in contrast to clinical trials, have the potential to offer valuable additional information with respect to real-life settings, such as durability of the regimen over longer periods of time. Cohort studies have evaluated the reasons for change of first-line regimen in the short term [10, 18] and long term [19] and the prevalence of use of different NNRTIs and PIs in first-line [12]. Nevertheless, durability of first-line ART and prognostic factors (either positive or negative) measured in current study, such as the probability of requiring ART switch, may have significant economic and public health relevance. Also durability can be highly influenced by local circumstances. Therefore, in this study, the durability of initial ART will be evaluated according to the third component in a cohort from Russia and association of baseline patient characteristics with treatment durability over a long period of time will be explored.

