## 2 Objectives and Hypotheses

### 2.1 Primary Objective

- To evaluate the 48 weeks treatment durability among treatment naive HIV-infected individuals initiated ART (NNRTI, PI) determined as a percentage of patients remained on initial therapy without change of the NNRTI or PI agent

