## 3 METHODOLOGY

### 3.1 Summary of Study Design

This study is a non-interventional retrospective study. Data from patients who signed informed consent form will be collected through retrospective chart or medical records review. Patients have been receiving treatment and diagnostic procedures according to daily clinical practice conducted by his/her physician. There are no procedures that are required as part of this study.

The study is to be conducted in up to 8 investigational sites across Russia with up to 200 patients recruited per site. Each investigational site will be a dedicated HIV clinic or an HIV department in clinic of infectious diseases. It is planned that the first half of the study population (500 patients) will be enrolled during the first 6-9 months and the second half of the study population (500 patients) during the second 6-9 months of the study.

HIV-infected patients with no experience of therapy at time of initiation of ART with NNRTI plus two NRTIs or PI boosted by ritonavir with 2 NRTIs will be enrolled and followed retrospectively for up to 96 weeks with data collection at the approximate time points of baseline (pre-treatment) and at 48 and 96 weeks after start of treatment.

The following ARV drugs are considered according to the standards of care:

- NNRTIs: efavirenz (EFV), nevirapine (NVP), rilpivirine (RPV), ETR (etravirine) etc.
- PIs: LPV (lopinavir), DRV (darunavir), ATV (atazanavir), FPV (fosamprenavir) etc.

All patients must have initiated ART between February 01 and June 30, 2017. A time window for the retrospective visits at baseline, 48 and 96 weeks is envisaged as approximately  $\pm$  8 weeks.

Patients will be retrospectively screened and selected according to inclusion and exclusion criteria prior to enrollment in each investigational site starting the day of its initiation. The study sites will maintain a list of all screened patients. All patients eligible according to the inclusion/exclusion criteria and after signing the informed consent form are to be consequently enrolled for their demographic and clinical data collection through retrospective chart or medical records review. The enrollment will continue until the recruitment goal is reached.

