### **3.2 Study Population**

All patients enrolled must be treatment naive at the time of initiation of ART with NNRTI plus two NRTIs or PI boosted by ritonavir with 2 NRTIs per the usual standard of care of the investigator in AIDS clinics of Russia.

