## 7.3 Sample Size and Power Calculations

There is no formal hypothesis testing the current study. Sample size justification is based on desired precision for the estimation of the primary variable – proportion of patients who continue the first line ART regimen at 48 weeks without changes.

The assumed 1-year discontinuation rate, based on published research, is 30% [20], therefore the assumed proportion of patients who remain on the first line ART regimen at 48 weeks is 70%. Precision (half-width of the 95% Wald confidence interval for the proportion) and 95% confidence intervals (CIs) for the proportion resulting from a range of sample sizes are presented in the table below:

Assumed Proportion	Patients enrolled	Patients with known status	95% CI Lower bound	95% CI Upper bound	95% CI Actual width (precision)
70.0%	250	250	64.3%	75.7%	11.4% ( $\pm 5.7\%$ )
70.0%	500	500	66.0%	74.0%	8.0% ( $\pm 4.0\%$ )
70.0%	750	750	66.7%	73.3%	6.6% ( $\pm 3.3\%$ )
70.0%	1000	1000	67.2%	72.8%	5.7% (<math>\pm 2.8\%</math>)
70.0%	1250	1250	67.5%	72.5%	5.1% ( $\pm 2.5\%$ )
70.0%	1500	1500	67.7%	72.3%	4.6% ( $\pm 2.3\%$ )

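### The 48- and 96-week multivariable logistic models leave out clinic, so their adjusted odds ratios for discontinuation may be confounded by clinic

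*Combined protocol and SAP*

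**What the plan says.** On recruitment, section 3.1 states: "The study is to be conducted in up to 8 investigational sites across Russia with up to 200 patients recruited per site". Section 5.3 has each centre enter its own data. Section 3.2 defines the patients as starting NNRTI or boosted PI plus two NRTIs "per the usual standard of care of the investigator in AIDS clinics of Russia".

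On aims, section 1.2 announces that "the durability of initial ART will be evaluated according to the third component in a cohort from Russia", together with an exploration of baseline characteristics. The same paragraph remarks that local conditions can affect durability strongly.

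On analysis, section 7.1.2 plans univariate and multivariable logistic regression at 48 and at 96 weeks to find risk factors for stopping initial ART, with unadjusted and adjusted odds ratios and 95% confidence intervals. A characteristic enters the multivariable model only if it passes univariate screening. The candidates are demographic and clinical characteristics; the cross-references point to 8.1.4 and 8.1.3, which I read as meaning the list in 7.1.3. That list has 13 factors, regimen class among them. Site is not one.

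On sample size, section 7.3 uses "Precision (half-width of the 95% Wald confidence interval for the proportion" and arrives at ±2.8 points. The protocol summary repeats this: "Inclusion of 1000 patients will allow the estimation of this proportion with 95% CI" of 67.2% to 72.8%.

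**The concern.** An adjusted odds ratio is meant to compare patients who are alike in other respects. Here patients are grouped in a handful of clinics, regimen choice follows each investigator's habits, and the rationale itself expects local conditions to matter. Clinic can therefore be linked both to a candidate factor and to the outcome, which is the condition for confounding. With no site term anywhere in sections 3.5 or 7.1 to 7.3, the models have no direct way to separate a regimen or patient effect from a difference between clinics. The bias and limitations text in 7.2 does not mention site either.

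At stake is the reading of the secondary association results. A clinic that both favours one class and retains patients better, for any reason, would make that class look more durable. The same applies to any patient characteristic spread unevenly over clinics.

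**Working it through.** **1. The plan's own figure.** Inputs from 7.3: proportion 0.70, n = 1000, 95% Wald interval. Half-width = 1.96 × √(0.70 × 0.30 / 1000) = 0.0284. The interval is 67.16% to 72.84%, width 5.68 points. This agrees with the stated 67.2% to 72.8%, 5.7% (±2.8%). The other five rows of the table also reproduce.

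**2. Number of clinics.** With a cap of 200 per site, 1000 patients need at least 1000/200 = 5 sites; the maximum is 8. A fixed site effect therefore uses 4 to 7 degrees of freedom.

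**3. Size of possible confounding.** The documents give neither discontinuation nor regimen mix by clinic, so all of these inputs are assumed except the overall 30% discontinuation and N = 1000. Half the patients (500) are in clinics with 34% discontinuation and half in clinics with 26%. Within each group NNRTI and PI do equally well (true odds ratio 1). PI users number 300 overall.

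| PI share, 34% clinics / 26% clinics | PI discontinuing | NNRTI discontinuing | Odds ratio without site |
|---|---|---|---|
| 20% / 40% | (100×0.34 + 200×0.26)/300 = 86/300 = 28.7% | (400×0.34 + 300×0.26)/700 = 214/700 = 30.6% | (86/214)/(214/486) = 0.91 |
| 40% / 20% | 94/300 = 31.3% | 206/700 = 29.4% | 1.09 |
| 10% / 50% | 82/300 = 27.3% | 218/700 = 31.1% | 0.83 |
| 50% / 10% | 98/300 = 32.7% | 202/700 = 28.9% | 1.20 |
| 30% / 30% | 90/300 = 30.0% | 210/700 = 30.0% | 1.00 |

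The last row shows that clinic differences in durability alone do not bias the odds ratio; regimen mix must differ too.

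**4. Bias against standard error.** For 20%/40%, the SE of the crude log odds ratio is √(1/86 + 1/214 + 1/214 + 1/486) = 0.152. The bias is |ln 0.913| = 0.091, or 0.6 SE. For 10%/50%, the SE is 0.153 and the bias |ln 0.832| = 0.184, or 1.2 SE.

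**5. Precision cost of adjusting.** Take the log odds ratio variance within each clinic group and combine by inverse variance. For 20%/40%:
- 34% clinics: 1/34 + 1/66 + 1/136 + 1/264 = 0.0557
- 26% clinics: 1/52 + 1/148 + 1/78 + 1/222 = 0.0433
- Combined SE = 1/√(1/0.0557 + 1/0.0433) = 0.156, against 0.152 without adjustment

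For 10%/50% the same steps give 0.171, against 0.153.

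**6. Model load.** Parameters from the 7.1.3 categories, with nine comorbidity indicators: 2+2+4+2+2+5+3+4+2+4+3+9+1 = 43. Expected discontinuations at 48 weeks: 0.30 × 1000 = 300. Events per parameter if every factor enters: 300/43 = 7.0 without site, 300/47 = 6.4 with 5 sites, 300/50 = 6.0 with 8.

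**The case against.** The strongest reply is that nothing in the documents shows that clinics differ in either durability or regimen mix. The rationale's remark on local conditions is qualitative and may contrast countries rather than clinics. The study tests no hypothesis, the models look only for potential risk factors, and NNRTI versus PI is one factor of 13 and not a stated comparison. In the milder example the bias is 0.6 of a standard error, and the larger one needs PI shares as far apart as 10% and 50%. The other baseline factors may also absorb part of any clinic difference. All of this stands, and it keeps the point conditional. It does not remove it: the plan promises adjusted odds ratios, clinic is an obvious thing to adjust for, and the variable should already be known.

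A second reply is that site burdens a model that may already be large. That is true if all 43 parameters enter, but the drop from 7.0 to 6.4 or 6.0 events per parameter is small, and screening may leave fewer terms. A remaining limit is that screening stays unadjusted, so a factor masked by clinic could still be dropped before the multivariable model.

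A reader might also infer that ±2.8% is wrong because it ignores clustering. The title ("Retrospective evaluation of treatment durability among treatment-naive HIV-infected individuals initiated first-line ART in Russia") and rationale ("To date, there is limited data on treatment durability in HIV infected individuals initiating ART in Russia") suggest a national target, and with an assumed intraclass correlation of 0.01 the half-width would be 2.84 × √(1 + 124 × 0.01) = ±4.25 with 8 equal sites, or 2.84 × √(1 + 199 × 0.01) = ±4.91 with 5. The documents do not support calling this an error. They give no intraclass correlation, and at 0.001 the same formula gives only ±3.01 and ±3.11. They do not say the clinics are a random sample of Russian clinics, which the formula requires. The primary objective ("To evaluate the 48 weeks treatment durability among treatment naive HIV-infected individuals initiated ART (NNRTI, PI") names no geographic target. The stated figure is correct for independent sampling error.

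**Conclusion.** The point holds as an inexpensive improvement to the secondary analysis. Both multivariable models omit clinic in a study of 5 to 8 clinics where regimen follows local practice. If a factor and durability both vary by clinic, the adjusted odds ratio for that factor is confounded, in a direction that cannot be predicted. Under the assumed inputs a true odds ratio of 1 appears as 0.91 or 1.09, and as 0.83 or 1.20 with more extreme regimen shares; with equal shares there is no bias. These sizes are illustrations, since the documents supply no clinic-level figures, and they assume that the other model terms do not carry the clinic difference.

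The ±2.8% and N = 1000 stand. The figure describes sampling error for the enrolled clinics' patients, weighted as they were enrolled and with known status. It does not describe variation between clinics across Russia, and section 7.3 does not claim that it does.

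**What to change.** - In 7.1.2, include site as a fixed effect in the 48- and 96-week multivariable logistic models, regardless of univariate screening. Leave the univariate odds ratios unadjusted, as the plan defines them.
- Set a threshold for pooling very small sites before the data are seen, which here means before the interim analysis at 500 patients.
- Report the 48- and 96-week percentages on initial therapy by site.
- At most, add one sentence to 7.3 and the protocol summary saying that ±2.8% reflects independent sampling error for the enrolled clinics' patients with known status, and not between-clinic variation across Russia. A table over assumed intraclass correlations and a clustered interval are not needed.

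Cost: SAP wording, one variable that should already be in the database, and one table. The models lose 4 to 7 degrees of freedom. In the examples the SE of the regimen log odds ratio rises from 0.152 to 0.156, or from 0.153 to 0.171 when regimen mix differs sharply between clinics. The sample size is unchanged.

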## 8 ADMINISTRATIVE AND REGULATORY DETAILS

### 8.1 Confidentiality

#### 8.1.1 Confidentiality of Data

By signing this protocol, the investigator affirms to the Sponsor that information furnished to the investigator by the Sponsor will be maintained in confidence, and such information will be divulged to the Institutional Review Board, Ethics Review Committee or similar or expert committee; affiliated institution and employees, only under an appropriate understanding of confidentiality with such board or committee, affiliated institution and employees. Data generated by this study will be considered confidential by the

investigator, except to the extent that it is included in a publication as provided in the Publications section of this protocol.

### **8.1.2 Confidentiality of Subject Records**

By signing this protocol, the investigator agrees that the Sponsor (or Sponsor representative), Institutional Review Board/Independent Ethics Committee (IRB/IEC), or Regulatory Agency representatives may consult and/or copy study documents in order to verify worksheet/case report form data. By signing the consent form, the subject agrees to this process. If study documents will be photocopied during the process of verifying worksheet/case report form information, the subject will be identified by unique code only; full names/initials will be masked prior to transmission to the Sponsor.

By signing this protocol, the investigator agrees to treat all subject data used and disclosed in connection with this study in accordance with all applicable privacy laws, rules and regulations.

### **8.1.3 Confidentiality of Investigator Information**

By signing this protocol, the investigator recognizes that certain personal identifying information with respect to the investigator, and all subinvestigators and study site personnel, may be used and disclosed for study management purposes, as part of a regulatory submissions, and as required by law. This information may include:

- name, address, telephone number and e-mail address;
- hospital or clinic address and telephone number;
- curriculum vitae or other summary of qualifications and credentials; and
- other professional documentation.

Consistent with the purposes described above, this information may be transmitted to the Sponsor, and subsidiaries, affiliates and agents of the Sponsor, in your country and other countries, including countries that do not have laws protecting such information. Additionally, the investigator's name and business contact information may be included when reporting certain serious adverse events to regulatory agencies or to other investigators. By signing this protocol, the investigator expressly consents to these uses and disclosures.

If this is a multicenter study, to facilitate contact between investigators, the Sponsor may share an investigator's name and contact information with other participating investigators upon request.

## **8.2 Compliance with Financial Disclosure Requirements**

Financial Disclosure requirements are outlined in the US Food and Drug Administration Regulations, Financial Disclosure by Clinical Investigators (21 CFR Part 54). It is the Sponsor's responsibility to determine, based on these regulations, whether a request for Financial Disclosure information is required. It is the investigator's/subinvestigator's responsibility to comply with any such request.

The investigator/subinvestigator(s) agree, if requested by the Sponsor in accordance with 21 CFR Part 54, to provide his/her financial interests in and/or arrangements with the Sponsor to allow for the submission of complete and accurate certification and disclosure statements. The investigator/subinvestigator(s) further agree to provide this information on a Certification/Disclosure Form, commonly known as a financial disclosure form, provided by the Sponsor or through a secure password-protected electronic portal provided by the Sponsor. The investigator/subinvestigator(s) also consent to the transmission of this information to the Sponsor in the United States for these purposes. This may involve the transmission of information to countries that do not have laws protecting personal data.

### **8.3 Compliance with Law, Audit and Debarment**

By signing this protocol, the investigator agrees to conduct the study in an efficient and diligent manner and in conformance with this protocol; generally accepted standards of Good Pharmacoepidemiology Practice and all applicable federal, state and local laws, rules and regulations relating to the conduct of the study.

The investigator also agrees to allow monitoring, audits, Institutional Review Board/Independent Ethics Committee review and regulatory agency inspection of study-related documents and procedures and provide for direct access to all study-related source data and documents.

The investigator agrees not to seek reimbursement from subjects, their insurance providers or from government programs for procedures included as part of the study reimbursed to the investigator by the Sponsor.

The Investigator shall prepare and maintain complete and accurate study documentation in compliance with Good Pharmacoepidemiology Practice, standards and applicable federal, state and local laws, rules and regulations; and, for each subject participating in the study, provide all data, and, upon completion or termination of the study, submit any other reports to the Sponsor as required by this protocol or as otherwise required pursuant to any agreement with the Sponsor.

Study documentation will be promptly and fully disclosed to the Sponsor by the investigator upon request and also shall be made available at the investigator's site upon request for inspection, copying, review and audit at reasonable times by representatives of the Sponsor or any regulatory agencies. The investigator agrees to promptly take any reasonable steps that are requested by the Sponsor as a result of an audit to cure deficiencies in the study documentation and worksheets/case report forms.

The investigator must maintain copies of all documentation and records relating to the conduct of the study in accordance with their institution's records retention schedule which is compliant with all applicable regional and national laws and regulatory requirements. If an institution does not have a records retention schedule to manage its records long-term, the investigator must maintain all documentation and records relating to the conduct of the study for 5 years after final report or first publication of study results, whichever comes

later, per GPP guidelines. This documentation includes, but is not limited to, the protocol, worksheets/case report forms, advertising for subject participation, adverse event reports, subject source data, correspondence with regulatory authorities and IRBs/ERCs, consent forms, investigator's curricula vitae, monitor visit logs, laboratory reference ranges, laboratory certification or quality control procedures and laboratory director curriculum vitae. All study documents shall be made available if required by relevant regulatory authorities. The investigator must consult with the Sponsor prior to discarding study and/or subject files.

The investigator will promptly inform the Sponsor of any regulatory agency inspection conducted for this study.

Persons debarred from conducting or working on studies by any court or regulatory agency will not be allowed to conduct or work on this Sponsor's studies. The investigator will immediately disclose in writing to the Sponsor if any person who is involved in conducting the study is debarred or if any proceeding for debarment is pending or, to the best of the investigator's knowledge, threatened.

In the event the Sponsor prematurely terminates a particular study site, the Sponsor will promptly notify that site's IRB/IEC.

According to European legislation, a Sponsor must designate an overall coordinating investigator for a multi-center study (including multinational). When more than one study site is open in an EU country, Merck, as the Sponsor, will designate, per country, a national principal coordinator (Protocol CI), responsible for coordinating the work of the principal investigators at the different sites in that Member State, according to national regulations. For a single-center study, the Protocol CI is the principal investigator. In addition, the Sponsor must designate a principal or coordinating investigator to review the study report that summarizes the study results and confirm that, to the best of his/her knowledge, the report accurately describes the conduct and results of the study in the study's final report. The Sponsor may consider one or more factors in the selection of the individual to serve as the Protocol CI and or CSR CI (e.g., availability of the CI during the anticipated review process, thorough understanding of study methods, appropriate enrollment of subject cohort, timely achievement of study milestones). The Protocol CI must be a participating study investigator.

